Section 12.1.10, Follow-up of AEs and SAEs	... Drug-induced liver injury may develop or progress even after the causative drug has been stopped. Results should be recorded in the CRF. Note that longer follow-up can sometimes reveal an off-drug repetition.	
Drug-Induced Liver Injury or Disease Progression
 
... Drug-induced liver injury may develop or progress even after the causative drug has been stopped. Results from drug induced liver injury follow-up should be recorded in the eCRF. Note that longer follow-up can sometimes reveal an off-drug repetition...
 
Cholecystitis or Pancreatitis
 
At the time of consent for new subjects (or re-consent to the protocol amendments for ongoing subjects), subjects will be instructed to contact the investigational site if they experience any of the following signs and symptoms: nausea, vomiting, abdominal pain, diarrhea, weight loss, fever and chills, worsening or new fatigue, or weakness. Subjects will also be counseled to seek immediate medical assistance if they experience persistent severe abdominal pain.
 
In the event that cholecystitis and/or pancreatitis is suspected, Investigators will be instructed to promptly bring subjects into the clinic to undergo a complete evaluation, including a physical examination, and laboratory assessments [ie, amylase and lipase]). Investigators should refer to standard of care guidelines on suspected pancreatitis (Banks 2012, Greenburg 2015). Diagnosis of acute pancreatitis includes 2 of the following:
 
 • Abdominal pain (acute onset of a persistent, severe, epigastric pain often radiating to the back) 	

Section	Original Text (Amendment 4, 10 May 2017)		Revised Text (Version 5, 04 Jan 2018)		Justification for Change
			
 • Serum lipase activity (or amylase) at least 3 times greater than the upper limit of normal • Characteristic findings of acute pancreatitis on computed tomography or magnetic resonance imaging 
To ensure appropriate vigilance, amylase and lipase levels will be monitored monthly for 3 months after onset of symptoms, irrespective of whether a diagnosis of cholecystitis and or pancreatitis is confirmed. Results should be recorded promptly in the eCRF.
		
Section 12.2.5, Dual Emission X-Ray Absorptiometry	12.2.5. Dual Emission X-Ray Absorptiometry A bone density assessment will be done using the DEXA scan.		Deleted		Procedure deleted
Section 12.2.6, Laboratory Assessments	Subjects will be instructed to attend each of their study visits (except Screening) in a fasted state,		Subjects will be instructed to attend any study or unscheduled laboratory visits (except Screening) in a fasted state,		Clarify subject should fast for all lab visits.
Section 12.2.6, Laboratory Assessments, Table 13	Laboratory Assessment	Analyte	Laboratory Assessment	Analyte	Labs added per FDA request
			Markers of Cholecystitis and Pancreatitis	amylase and lipase	
	Blood Sample for Future Analysis	PBC autoantibodies and other cytokines and interleukins TBD			Procedure deleted
Section 12.2.6, Laboratory Assessments,	MELD scores, Child-Pugh score, and MRS will be calculated at screening, and at quarterly (MELD and Child-Pugh scores) or semi-annual (MRS) visits based on serum chemistry and coagulation.		MELD scores and Child-Pugh score will be calculated at screening, and at all visits based on serum chemistry and coagulation.		Clarify subject should fast for all lab visits
Section 13.2.1, Safety Analyses, Adverse Events	Insertion		Adverse events of special interest as described in Section 12.1.1.4 will be summarized for each treatment group. In addition, each event is a		Per FDA request.

Section	Original Text (Amendment 4, 10 May 2017)	Revised Text (Version 5, 04 Jan 2018)	Justification for Change
		
component of the primary endpoint, and will be summarized as secondary endpoints as described in Section 13.1.4.
	

Section 13.4, Adjudication Committees
	
All suspected liver-related clinical outcomes, MACE/Expanded MACE, and drug-related hepatic injury events that occur after administration of the first dose of investigational product will be reviewed by the following blinded adjudication committees, depending on event type, before inclusion in any analysis. The 3 committees and event types they are responsible for adjudicating are as follows:
 
 • Cardiovascular Adjudication Committee (CAC): Adjudicates all suspected MACE, including all deaths • Hepatic Outcomes Committee: Adjudicates all deaths and suspected liver-related outcomes • Hepatic Safety Committee: Adjudicates all suspected drug-related hepatic injury events 
Each adjudication committee will have a charter that documents the reporting of events by the study site, definition of the suspected events to be adjudicated, supply of source documentation to the committee,
	
All suspected liver-related clinical outcomes and MACE/Expanded MACE that occur after administration of the first dose of investigational product will be reviewed by the following blinded adjudication committees, depending on event type, before inclusion in any analysis. The 2 committees and event types they are responsible for adjudicating are as follows:
 
 • Cardiovascular Adjudication Committee (CAC): Adjudicates all suspected MACE, including all deaths • Hepatic Outcomes Committee: Adjudicates all deaths and suspected liver-related outcomes 
Each adjudication committee will have a charter that documents the reporting of events by the study site, definition of the suspected events to be adjudicated, supply of source documentation to the committee,
	
There is no longer a need for the Hepatic Safety Committee given the updated guidance for the Investigator.

References
		
 
	

Section	Original Text (Amendment 4, 10 May 2017)	Revised Text (Version 5, 04 Jan 2018)	Justification for Change
		
 
	

Appendix A, Overview of Modified Dosing Regimen for Subjects with Child-Pugh B or C Hepatic Impairment
	
... Overview of Modified Dosing Regimen for Subjects with Child-Pugh B or C Hepatic Impairment
 
An overview of the modified dosing regimen for subjects with Child-Pugh Class B or Child-Pugh Class C is presented in and.
 
Subjects who are cirrhotic and classified as Child-Pugh Class B or Child-Pugh Class C will initiate a modified treatment regimen with 5 mg OCA or matching placebo once weekly for at least 3 months. Subjects classified as Child-Pugh Class B should eventually titrate to a maximum dose of 5 mg OCA or matching placebo once daily, based on tolerability and biochemical response. Subjects classified as Child-Pugh Class C should titrate to a maximum dose and frequency of 10 mg OCA or matching placebo twice weekly.
	
Subjects with cirrhosis and classified as Child-Pugh B or Child-Pugh C at Screening will follow a modified dosing schedule initiating 5 mg OCA or matching placebo once weekly as described in Figure 3. After a minimum of 3 months dosing once weekly with 5 mg OCA or matching placebo, and following review of the pre-titration laboratory results to assess safety and tolerability, the dosing frequency of 5 mg OCA or matching placebo should be increased to twice weekly (at least three days apart). Subjects who have maintained the twice weekly dosing frequency for a minimum of at least 6 weeks, and meet the dose titration criteria, should up titrate to the maximum allowed dose of 10 mg OCA or matching placebo twice weekly (Table 14). Investigators may decrease the dosing frequency (back to once weekly) or dose for any subject at any time during the study, as considered clinically appropriate (eg, tolerability).
	
Deleted overview section and replaced with text


Appendix A, Figure 3
	 
<small>**Cirrhosis may be assessed by histology or non-histological methods as defined in Section 9.7.3. RTW = once weekly; QW = once weekly</small>
	 
<small>**Cirrhosis may be assessed by histology or non-histological methods as defined in Section 7.5.4. RTW = once weekly; QW = once weekly</small>
	
Same dosing scheme for CP-B and CP-C subjects.

Section	Original Text (Amendment 4, 10 May 2017)	Revised Text (Version 5, 04 Jan 2018)	Justification for Change																																					
Appendix A, Table 14	
  
 	Planned Dosing Regimen^a	
 
 Standard^b Noncirrhotic^c Child-Pugh A^d	Modified^e Child-Pugh B^d	Child-Pugh C^d	
   
 • Starting Dose^f (Day 0)	5 mg daily	5 mg once weekly	5 mg once weekly	
 
 • Titration 1^g (Month 3)	10 mg daily	5 mg twice weekly	5 mg twice weekly	
 
 • Titration 2^h (≥6 weeks after Titration 1)	NA	10 mg twice weekly	10 mg twice weekly	
 
 • Titration 3^h (≥6 weeks after Titration 2)	NA	5 mg daily	NA	
  
		Planned Dosing Regimen ^a			Standard ^b Noncirrhotic ^c Child-Pugh A ^d	Modified ^e Child-Pugh B ^d	Child-Pugh C ^d	• Starting Dose ^f (Day 0)	5 mg daily	5 mg once weekly	5 mg once weekly	• Titration 1 ^g (Month 3)	10 mg daily	5 mg twice weekly	5 mg twice weekly	• Titration 2 ^h (≥6 weeks after Titration 1)	NA	10 mg twice weekly	10 mg twice weekly	• Titration 3 ^h (≥6 weeks after Titration 2)	NA	5 mg daily	NA	
  
 	Planned Dosing Regimen^a	
 
 Standard^b Noncirrhotic^c Child-Pugh A^d	Modified^e Child-Pugh B or C^d	
   
 • Starting Dose^f (Day 0)	5 mg daily	5 mg once weekly	
 
 • Titration 1^g (Month 3)	10 mg daily	5 mg twice weekly	
 
 • Titration 2^h (≥6 weeks after Titration 1)	NA	10 mg twice weekly	
  
 
<small>^a Starting dose based on subject's cirrhotic status and Child-Pugh Score at Screening. ^b</small>
		Planned Dosing Regimen ^a		Standard ^b Noncirrhotic ^c Child-Pugh A ^d	Modified ^e Child-Pugh B or C ^d	• Starting Dose ^f (Day 0)	5 mg daily	5 mg once weekly	• Titration 1 ^g (Month 3)	10 mg daily	5 mg twice weekly	• Titration 2 ^h (≥6 weeks after Titration 1)	NA	10 mg twice weekly	Titration #3 is no longer applicable to study. To align with label, maximum dose for Child-Pugh B or C subjects is 10 mg OCA twice weekly.
	Planned Dosing Regimen ^a																																							
	Standard ^b Noncirrhotic ^c Child-Pugh A ^d	Modified ^e Child-Pugh B ^d	Child-Pugh C ^d																																					
• Starting Dose ^f (Day 0)	5 mg daily	5 mg once weekly	5 mg once weekly																																					
• Titration 1 ^g (Month 3)	10 mg daily	5 mg twice weekly	5 mg twice weekly																																					
• Titration 2 ^h (≥6 weeks after Titration 1)	NA	10 mg twice weekly	10 mg twice weekly																																					
• Titration 3 ^h (≥6 weeks after Titration 2)	NA	5 mg daily	NA																																					
	Planned Dosing Regimen ^a																																							
	Standard ^b Noncirrhotic ^c Child-Pugh A ^d	Modified ^e Child-Pugh B or C ^d																																						
• Starting Dose ^f (Day 0)	5 mg daily	5 mg once weekly																																						
• Titration 1 ^g (Month 3)	10 mg daily	5 mg twice weekly																																						
• Titration 2 ^h (≥6 weeks after Titration 1)	NA	10 mg twice weekly																																						
Appendix A	
Modified Dosing Regimen for Subjects with Child-Pugh B Hepatic Impairment Subjects with cirrhosis and classified as Child-Pugh BC at Screening will follow a modified dosing schedule receiving 5 mg OCA or matching placebo once weekly as described in . After a minimum of 3 months dosing once weekly with 5 mg OCA or matching placebo, and following review of the pre-titration laboratory results to assess safety and tolerability, the dosing frequency of 5 mg OCA or matching placebo should be increased to twice weekly (at least 3 days apart). Subjects who have maintained the twice weekly dosing frequency for a minimum of at least 6 weeks, and meet the dose titration criteria, should up-titrate to twice weekly dosing with 10 mg OCA or matching placebo. Subjects with at least 6 weeks of twice weekly dosing at 10 mg OCA or matching placebo, and meeting dose titration criteria, should up-titrate to the maximum allowed dose of 5 mg OCA or matching placebo once daily. Investigators may decrease the dosing frequency (back to once or twice weekly) or dose for any subject at any time during the study, as considered clinically appropriate (eg, tolerability).
																																							
Appendix A, Dose Titration due to Change in	
Subjects on a modified dosing regimen who demonstrate a change in cirrhosis status 7.5.4 and/or Child-Pugh Score 7.5.5 should have their dose of investigational product modified to match
	
When subjects demonstrate a change in cirrhosis status (as assessed per Section 7.5.4) or Child-Pugh Score (Section 7.5.5 dosing should be reassessed and the dosing regimen modified appropriately.
																																						

Section	Original Text (Amendment 4, 10 May 2017)	Revised Text (Version 5, 04 Jan 2018)	Justification for Change
Cirrhosis or Child-Pugh Score	
their current status per the appropriate dosing regimen (see Section ,); however, changes to the dosing regimen are not mandatory and should be based on clinical judgment as well as changes in status. Changes in Child-Pugh Score that result from a transient, explainable change in laboratory parameters should be documented appropriately, and should not necessarily result in a change to the dosing regimen. Investigators may contact the Medical Monitor at any time to discuss potential changes to dosing.
 
Possible scenarios for dosing modifications include:
 
 • Subjects who develop cirrhosis during the course of the trial with a classification of Child-Pugh B or C • Subjects with pre-existing cirrhosis who demonstrate a change in the Child-Pugh Score from A to B or C at any point in the study • Improvement in classification of Child-Pugh Score from C to B • Improvement in classification of Child-Pugh Score from B to A; these subjects may be eligible to transition to the standard dosing regimen 
Subjects may titrate dose and dosing frequency up or down as appropriate, within the appropriate dosing regimen. Up-titration should be done per Investigator discretion and be guided by the pre-titration tolerability assessments outlined in Section 7.4.1. A 1-Month Post-Titration Assessment must be performed any time a subject's dose or frequency is up-titrated (see Section 7.1.2 and Section 9.7.10).
	
Changes in Child-Pugh Score that result from a transient, explainable change in laboratory parameters (eg, increase in INR due to vitamin K deficiency) should be documented appropriately and discussed with the Medical Monitor before any continuation or change to the dosing regimen. Possible scenarios for dosing modifications include:
 
 • Subjects who develop cirrhosis during the course of the trial with a classification of Child-Pugh B or C • Subjects with pre-existing cirrhosis who demonstrate a change in the Child-Pugh Score from A to B or C at any point in the study 
Subjects may titrate dose and dosing frequency up or down as appropriate, within the dosing regimen. Up-titration should be done per Investigator discretion and be guided by the pre-titration tolerability assessments outlined in Section 7.4.1. A 1-Month and 2-Month Post-Titration Assessment must be performed any time a subject's dose or frequency is up-titrated (see Section 7.1.2 and Section 9.7.7).
	
Appendix A, Unscheduled	
...: The \pm 1 week window week related to the 1-month Post-Titration Visit can be extended for up to an additional 5 weeks to allow for the post-
	
...: The \pm1 week window related to the 2-month Post-Titration Visit can be modified to occur 2 weeks earlier or 2 weeks outside of the allowed
	

Section	Original Text (Amendment 4, 10 May 2017)	Revised Text (Version 5, 04 Jan 2018)	Justification for Change
Titration Visit, Optional Visit	titration assessment to be performed during one of the subject’s regularly scheduled study visits. If the window is extended past +1 week allowed visit window, at a minimum, a telephone safety contact should then be performed 1-month post-titration.	visit window to allow for the post-titration assessment to be performed during one of the subject’s regularly scheduled study visits. If the 2-month Post-Titration Visit is performed during a regularly scheduled study visit, all scheduled procedures associated with that visit should be performed.	

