Study Personnel Contact Information	
Or if Not Available:
 
Contact: PPD [redacted] MD, PhD Medical Director, Clinical Research, Intercept Pharmaceuticals, Inc.
 
Telephone: PPD [redacted]
 
Mobile: PPD [redacted] (Pacific time zone)
 
Email: PPD [redacted] PPD [redacted]
 
Clinical Operations and Project Management
 
Contact: PPD [redacted] PPD Clinical Operations, Intercept Pharmaceuticals, Inc.
 
Telephone: PPD [redacted] (Pacific time zone)
 
Mobile: PPD [redacted]
 
Fax: PPD [redacted]
 
Email: PPD [redacted] PPD [redacted]
		
Updating emergency medical monitor contact information.
 
The contact information for clinical operations and project management personnel is no longer required in the protocol per Sponsor’s procedures.

Synopsis, Objectives, Primary, Statistical Methods – Efficacy Analyses	
To assess the effect of OCA compared to placebo, in conjunction with established local standard of care, on clinical outcomes in subjects with primary biliary cirrhosis (PBC) as measured by time to first occurrence of any of the following adjudicated events, derived as a composite event endpoint:
	
To assess the effect of OCA compared to placebo, in conjunction with established local standard of care, on clinical outcomes in subjects with primary biliary cholangitis (PBC) as measured by time to first occurrence of any of the following adjudicated events, derived as a composite event endpoint:
	
Editorial correction
 
HCC has been redefined as a secondary endpoint instead of a component of the primary

Section	Original Text (Amendment 3.1, 21 December 2016)	Revised Text (Version 4, 10 May 2017)	Justification for Change

Section 6.1 Primary Objective
 
Section 11.1.1 Primary Assessments
 
Section 13.1.3 Primary Efficacy Analysis
	
● Hepatocellular carcinoma confirmed by 2 complimentary imaging modalities unless confirmed by biopsy
		
composite-event endpoint per Regulatory Authority request.

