Clinical outcomes	
 - Encephalopathy (as defined by a West Haven score of ≥ 2) • Hepatocellular carcinoma confirmed by 2 complimentary imaging modalities 																		
Secondary Objectives																			
Primary Objectives	Assessments																		
Clinical outcomes	- Hepatic encephalopathy (as defined by a West Haven score of ≥ 2)																		
Secondary Objectives																			
Progression to cirrhosis	Clinical, laboratory, or radiological evidence of cirrhosis and/or liver stiffness (i.e., Fibroscan® TE) confirmed by biopsy unless not medically indicated																		
Hepatocellular carcinoma	Confirmed by 2 complimentary imaging modalities unless confirmed by biopsy																		
Synopsis , Statistical Methods Analysis Populations	The following subject populations will be evaluated and used for presentation and analysis of the data: Randomized , Intent-to-Treat (ITT), Safety, PK, Overall Historical Control, UKPBC Historical Control, and the Global PBS Historical Control. Descriptions of subject populations are provided in Section 13.1.1.	The following subject populations will be evaluated and used for presentation and analysis of the data: Intent-to-Treat (ITT), Per Protocol (PP) Safety, PK, Overall Historical Control, UK-PBC Historical Control, and the Global PBS Historical Control. Descriptions of subject populations are provided in Section 13.1.1.	Randomized population includes patients on OCA who withdrew prior to receiving drug and this is already collected with the safety population. Rationale 12 (for PP Population)																

Section	Original Text (Amendment 3, 07 September 2016)	Revised Text (Version 4, 10 May 2017)	Justification for Change

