
Synopsis, Statistical Methods, Primary Efficacy Endpoint
 
Section 11.1.1 Primary Assessments
	
The primary efficacy endpoint will be the time to first occurrence of one of the following post randomization:
 
 • Encephalopathy (as defined by a West Haven score of ≥ 2) • Hepatocellular carcinoma confirmed by 2 complimentary imaging modalities 
Change in Synopsis section Every event for enrolled subjects will be adjudicated by an independent committee.
	
The primary efficacy endpoint will be the time to first occurrence of one of the following:
 
 • Hepatic encephalopathy (as defined by a West Haven score of ≥ 2) 
All events will be adjudicated by an independent committee.
	
Rationale 5

Synopsis, Statistical Methods, Primary Efficacy Analysis
 
Section 13.1.3 Primary Efficacy Analysis
	
The primary efficacy analysis will compare randomized OCA to randomized placebo with respect to the primary efficacy endpoint using the ITT population.
 
Insertion
	
The primary efficacy analysis will compare OCA to placebo with respect to the primary efficacy endpoint using the ITT population.
 
The same analyses for primary efficacy endpoints will be performed for PP population as a sensitivity analysis.
	
Rationale 12

Synopsis, Statistical Methods, Key Secondary Efficacy Analyses
 
Section 13.1.4 Secondary Efficacy Analysis
	
The key secondary efficacy analyses will compare randomized OCA to randomized placebo in ITT population with respect to the key secondary efficacy endpoints.
 
Insertion
	
The key secondary efficacy analyses will compare OCA to placebo in the ITT population with respect to the key secondary efficacy endpoints.
 
The same analyses for key secondary efficacy endpoints will be performed for PP population as a sensitivity analysis.
	
Rationale 12

Synopsis, Statistical Methods, Additional Efficacy Analyses
	
Other Efficacy Analyses
 
The following secondary efficacy analyses will compare OCA to placebo on time to the following events:
	
Additional Efficacy Analyses
 
The following time-to-event secondary efficacy analyses will compare OCA to placebo using the ITT population:
 
 • Progression to cirrhosis • Time to occurrence of HCC 	
Rationale 6 and Rationale 11

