
Section 13 Statistical Methods
	
A statistical analysis plan (SAP), providing details about the specific planned analyses and hypothesis tests, will be prepared and approved by the Sponsor and its designees prior to study database lock, propensity score determination, and unblinding of the double-blind subject treatment assignments.
	
A statistical analysis plan (SAP), providing details about the specific planned analyses and hypothesis tests, will be prepared and approved by the Sponsor and its designees prior to the first interim analysis, propensity score determination, and unblinding of the double-blind subject treatment assignments.
	
Reflects addition of interim analyses to the study protocol.
								

Section	Original Text (Amendment 3, 07 September 2016)	Revised Text (Version 4, 10 May 2017)	Justification for Change

Section 13.1.1 Analysis Populations
	
• The Randomized Population will include all randomized subjects
 
Insertion
	
Deletion
 
 • The Per Protocol (PP) Population will include all ITT subjects who do not have any major protocol violations that potentially affect the efficacy conclusion. Treatment assignment will be based on the randomized treatment. 	
Rationale 12

Section 13.1.1.1 Comparability of Historical Controls
	
Historical controls from both databases will be chosen based on the same study inclusion/exclusion criteria where possible.
	
Historical controls from both databases will be chosen based on the same study inclusion/exclusion criteria. Propensity score matching method will be utilized to select historical controls that match the treated subjects using available covariates. The adequacy of matching will be assessed by statistical methods described under Section 13.1.8.
	
Clarifies the use of propensity scores in the assessment of the historical control population.

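### Section 13.4 starts adjudication at first dose, while the endpoint text has all events adjudicated and the primary analysis is labelled ITT; the three should be aligned on randomization

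*Protocol*

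**What the plan says.** The body text of these sections is not in the part of the protocol available, so the revised columns of the change tables are used.

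- **Section 13.4, Version 5 (Appendix J).** Suspected liver-related outcomes and cardiovascular events "that occur after administration of the first dose of investigational product will be reviewed by the following blinded adjudication committees", and that review must precede their use in an analysis. The two committee bullets, each of which includes all deaths, stand under that sentence. The Version 6 table (Appendix K) lists no change to 13.4.
- **Primary objective, Version 4 (Appendix H).** The effect is assessed "as measured by time to first occurrence of any of the following adjudicated events, derived as a composite event endpoint".
- **Primary endpoint, synopsis, Version 4 (Appendix I).** "All events will be adjudicated by an independent committee". No first-dose condition is attached.
- **Section 13.1.3, Version 4 (Appendix I).** "The primary efficacy analysis will compare OCA to placebo with respect to the primary efficacy endpoint using the ITT population".
- **Analysis populations, Version 4 (Appendix I).** The separate Randomized Population was deleted from Section 13.1.1. The synopsis row gives as the reason: "Randomized population includes patients on OCA who withdrew prior to receiving drug and this is already collected with the safety population".
- **Section 7.1, Version 4 (Appendix I).** The study runs until about 127 adjudicated primary endpoint events have accrued, so the same adjudicated count also decides when it ends.

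**The concern.** An ITT analysis of a time-to-event outcome counts events from randomization in everyone randomized. Section 13.4 attaches a later condition, receipt of a first dose, to the step that turns a suspected event into a countable one. A subject who is randomized but never dosed has no time after first dose, so 13.4 provides no route to adjudication for any event in that subject. The justification for deleting the Randomized Population acknowledges that such subjects can exist.

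Two things are at stake. One is an internal conflict: one place adjudicates all events and another adjudicates only those after first dose. The other is whether the ITT label on the primary analysis describes what will be counted. The place to settle this is the protocol and charter, because source documents for events that were never sent to a committee are hard to collect after the fact.

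**Working it through.** **Step 1. Which subjects are affected.** The change table for Amendment 1 (Section 9.7.1) makes Day 0 the day of randomization and Day 1 the day of first dose. For dosed subjects the gap is one day. With placebo survival 0.6 at 8 years (Section 13.1.2, Appendix I), the placebo hazard is λ0 = −ln(0.6)/8 = 0.0639 per year. Expected events in the gap, even with everyone at that hazard, are 428 × 0.0639/365.25 = 0.07. Only never-dosed subjects matter.

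**Step 2. Reproduce the plan's figures.** Inputs from Section 13.1.2: hazard ratio 0.60, 4 years of accrual, 6 years of follow-up, 10% dropout, 428 subjects, 127 events, 80% power, interim looks at 50% and 75%. The significance level is not given in the part available; 0.05 two-sided is assumed.

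- λ1 = 0.6 × 0.0639 = 0.0383 per year.
- Event probability with follow-up uniform on 6 to 10 years: P(λ) = 1 − [exp(−6λ) − exp(−10λ)]/(4λ). This gives 0.398 on placebo, 0.263 on OCA, mean 0.331.
- Expected events: 428 × 0.331 = 141.6 without dropout; × 0.9 = 127.4, against the stated 127.
- Power at 127 events with Lan-DeMets O'Brien-Fleming boundaries (z = 2.963, 2.359, 2.014) is 81.3%, against the stated 80%.

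The plan's figures reproduce; none of them is contested here.

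**Step 3. Size of the effect.** The documents do not give the never-dosed share f, so a range is shown. *Pro rata* events are 127f. *Full follow-up* events are 428f × 0.331. The all-randomized hazard ratio is approximated by (1 − f) × 0.60 + f × 1, on the assumption that never-dosed OCA subjects carry the placebo hazard. Power is at 127 events with the two looks.

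| f (assumed) | Never dosed | Events, pro rata | Events, full follow-up | Hazard ratio if counted | Power |
|---|---|---|---|---|---|
| 0.2% | 0.9 | 0.3 | 0.3 | 0.601 | 81.2% |
| 1% | 4.3 | 1.3 | 1.4 | 0.604 | 80.3% |
| 2% | 8.6 | 2.5 | 2.8 | 0.608 | 79.3% |
| 5% | 21.4 | 6.4 | 7.1 | 0.620 | 76.0% |

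If every never-dosed subject had the placebo event probability of 0.398, the 1% and 2% rows would give 1.7 and 3.4 events.

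**Step 4. The two possible ITT definitions.**

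- *ITT is all randomized.* Never-dosed subjects stay in the risk set, but 13.4 supplies no adjudicated event for them.
- *ITT requires a dose.* Section 13.4 and the population agree with each other. The ITT label is then inaccurate, and an edit to 13.4 alone brings nobody into the primary analysis.

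The text does not settle which applies. Before Version 4 there was a separate population: "The Randomized Population will include all randomized subjects". Keeping it apart from ITT hints that ITT may have required a dose, but that is only a hint. Either way, something needs correcting.

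**The case against.** A reader might infer that events in never-dosed subjects can never be adjudicated and that the primary analysis is therefore shown not to be ITT. The documents do not support that. Section 13.4 says what will be reviewed; it does not say that other events are barred. The endpoint text has all events adjudicated, and each committee's charter, which defines the events to be adjudicated, is not shown. Nor is the ITT definition. What stands is narrower: the two statements differ and, read literally, 13.4 leaves these events out.

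A reader might also infer a bias in favour of OCA. The trial is double-blind with matching placebo and dosing starts the day after randomization, so failure to take a first dose should be largely unrelated to arm.

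The event count is also at the upper end. The subjects the protocol mentions are those who withdrew before receiving drug. Under Table 8 (Appendix K, Section 9.7.15), full withdrawal of consent means no further visits beyond the end-of-treatment/end-of-study visit. Many of them might yield no observable event under any adjudication rule. This objection stands and is reflected in the verdict.

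Finally, the quoted 13.4 wording is from the Version 5 table, and the Version 6 table does not list minor edits individually. That the wording persists is likely but inferred.

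**Conclusion.** The point holds as an inconsistency of minor weight. Section 13.4 starts adjudication at first dose, the endpoint text sets no such limit, and the ITT label implies counting from randomization. Under either possible ITT definition, one of these texts has to change.

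The size is about 1 to 3 of 127 events if 1–2% of 428 subjects are never dosed and all are followed. Both conditions are assumptions, and the true number may be near zero. At that share, counting the events would move the planned hazard ratio from 0.600 to about 0.604–0.608 and power from 81.3% to 80.3–79.3%. No design conclusion changes, and no directional bias is shown.

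**What to change.** 1. In Section 13.4 and the hepatic outcomes charter, start adjudication of suspected hepatic outcomes and of all deaths at randomization, for all randomized subjects.
2. Make this agree with the endpoint statement that all events are adjudicated, so that one rule appears throughout.
3. In Section 13.1.1, confirm that the ITT population is all randomized subjects. If it requires a dose, relabel it as modified ITT and add an all-randomized analysis of the primary endpoint.
4. Keep first dose as the start for safety summaries.

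The cost is a short wording change in the protocol and charter, plus one extra run of the primary analysis if the population is relabelled. Dosing, visits and clinical rules are not affected.
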